7.7.6 Pre-IVL Dilatation of Target Lesion & Crossover (if required)

If the operator is unable to cross the JAVELIN IVL Catheter through the entire length of the target lesion, a standard PTA balloon up to 2.5 mm may be used for pre-dilatation of the target lesion prior to treatment with the JAVELIN IVL Catheter. All efforts should be made to pass the JAVELIN IVL Catheter prior to use of a standard PTA balloon.

If the operator is unable to pass the JAVELIN IVL Catheter after pre-dilatation, the operator may attempt to cross with the alternate JAVELIN IVL Catheter configuration (crossover). Note: if the operator has already used the alternate configuration (prior crossover per Section 7.7.5), a second crossover is not permitted. All crossovers should be documented.

If the user is unable to advance any JAVELIN IVL Catheter across the target lesion, this is considered an **IVL Device Failure**. Treatment should continue per standard of care for the subject.

7.7.7 IVL Treatment

Once the JAVELIN IVL Catheter is placed in the target lesion area, the catheter must be pressurized to 4 atm to deliver one cycle of IVL pulses. Table 2 lists the pulsing sequence for the JAVELIN IVL Catheter. One cycle = 10 pulses. The catheter is able to deliver total of 12 cycles (120 pulses). Note that the generator is programmed to force a minimum pause time of 10 seconds following every cycle.

No.: CP 67398

REV. C

TITLE: FORWARD PAD IDE Study Protocol

CLASS: CLINICAL PROTOCOL

PAGE 29 OF 65

Following delivery of the first IVL cycle, record lesion response on fluoroscopy. Before delivering the next treatment cycle, open the outlet port and pressurize to 6 atm to flush the system with saline.

Repeat the steps above to deliver additional pulses of IVL. Multiple locations should be treated for long lesions. For optimal results, treat the entire lesion length with IVL; do not use “spot” IVL. **Caution:** Care must be taken not to exceed 120 pulses in the same segment.

Following initial treatment with the JAVELIN IVL Catheter, the 2nd required angiographic cine (Post-JAVELIN) should be acquired.

Table 2. JAVELIN IVL System Sequence Chart

	JAVELIN
Treatment Frequency	1 Pulse per Second
Maximum Number of Continuous Pulses (1 cycle)	10 Pulses
Minimum Pause Time (between cycles)	10 Seconds
Maximum Total Pulses Per Catheter	120 (12 Cycles)

7.7.8 Post-Dilatation (Mandatory)

Post-dilatation with a semi or non-compliant PTA balloon catheter must be completed at nominal pressure.

The physician should use a 1:1 balloon catheter to artery ratio and may dilate for several minutes. Follow the angiographic core lab guidelines to complete angiography showing all target lesions with reproducible landmarks for follow-up evaluation and assessment.

Following mandatory post-dilatation, the 3rd required angiographic image (Post-Dil) should be acquired.

7.7.9 Additional Target Lesion Treatment (if required)

Following mandatory post-dilatation, additional IVL treatment may be delivered if areas of non-dilatable residual stenosis > 50% remain. This may be done using the commercially available Shockwave M⁵, M⁵⁺ or S⁴ IVL catheters – or additional pulses with the same JAVELIN IVL catheter configuration used for treatment in section 7.7.7 may be delivered.

7.7.10 Destination Therapy

Destination therapy is allowed at the discretion of the Investigator. Destination therapy may include commercial IVL, bare-metal stent (BMS), drug-eluting stent (DES), drug coated balloon (DCB) or Tack implant.

 SHOCKWAVE <small>MEDICAL INC</small>	No.: CP 67398	REV. C
	TITLE: FORWARD PAD IDE Study Protocol	
	CLASS: CLINICAL PROTOCOL	PAGE 30 OF 65

A. BMS, DES, DCB or Tack implant is allowed for the following PTA failures:

- Residual stenosis \geq 50% by visual estimate, or
- Un-resolved flow-limiting (\geq Grade D) dissection, or
- Trans-lesional gradient >10 mm Hg is observed.

If this treatment is performed at the time of procedure, it is considered standard of care to maximize acute luminal gain and does not meet the definition of serious deterioration in the SAE definition (Section 10.1.2).

All dissection Type/Grade A, B, and C must be documented as an adverse event. Dissection Type/Grade D, E, and F must be documented as a SAE.

The 4th and final required angiographic cine should be acquired after all endovascular procedures on the target lesion are complete.

7.8 Follow-Up

7.8.1 Discharge or Within 12-24 Hours Post-Procedure

The following assessments and procedures will be performed within **12-24 hours** post procedure or prior to hospital discharge, whichever occurs first:

- Review of anticoagulation/antiplatelet medications
- Adverse event assessment

7.8.2 30-Day Follow-Up

The following evaluations will be performed at **30 days** (-7/+14 days) post procedure:

- Physical examination
 - Vital signs
- ABI or TBI of target limb (at rest; keep consistent with screening)
- Rutherford Category of target limb
- Review of anticoagulation/antiplatelet medications
- Adverse event assessment

Note: If treatment of two target lesions is planned across both limbs, the Rutherford Category and ABI/TBI for each limb must be assessed. If ABI/TBI cannot be assessed due to non-compressible vessels, this should be documented.

7.8.3 6-Month Follow-Up

The following evaluations will be performed at **6 months** (180 +/-30 days) post procedure:

- Physical examination
 - Vital signs
- ABI or TBI of target limb (at rest; keep consistent with screening)

 SHOCKWAVE <small>MEDICAL INC</small>	No.: CP 67398	REV. C
	TITLE: FORWARD PAD IDE Study Protocol	
	CLASS: CLINICAL PROTOCOL	PAGE 31 OF 65

- Rutherford Category of target limb
- Review of anticoagulation/antiplatelet medications
- Adverse event assessment

Note: If treatment of two target lesions is planned across both limbs, the Rutherford Category and ABI/TBI for each limb must be assessed. If ABI/TBI cannot be assessed due to non-compressible vessels, this should be documented.

7.8.4 12-Month Follow-Up

The following evaluations will be performed at **12 months** (360 +/-30 days) post procedure:

- Physical examination
 - Vital signs
- ABI or TBI of target limb (at rest; keep consistent with screening)
- Rutherford Category of target limb
- Review of anticoagulation/antiplatelet medications
- Adverse event assessment
- Duplex ultrasound (DUS)

Note: If treatment of two target lesions is planned across both limbs, the Rutherford Category and ABI/TBI for each limb must be assessed. If ABI/TBI cannot be assessed due to non-compressible vessels, this should be documented.

7.8.5 Prior to Target Limb Revascularization

If a target limb revascularization procedure is performed during the follow-up period, angiographic images acquired as standard of care should be submitted to the core lab for purposes of adjudication.

7.9 Subject Withdrawal

A study subject has the right to discontinue participation at any time without penalty or loss of benefits to which the subject is otherwise entitled. A subject that has withdrawn from the study will be treated according to standard of medical care and will not be replaced.

7.9.1 When and How to Withdraw Subjects

Subjects may be withdrawn with the medical discretion of the physician, or they may voluntarily withdraw their consent at any time without impact to their medical treatment. When a subject is withdrawn, all data obtained prior to the time of withdrawal may be submitted to the Study Sponsor and be included in the study database, unless otherwise requested by the subject in writing.

 SHOCKWAVE MEDICAL INC.	No.: CP 67398	REV. C
	TITLE: FORWARD PAD IDE Study Protocol	
	CLASS: CLINICAL PROTOCOL	PAGE 32 OF 65

In the event a subject is lost to follow-up or cannot be contacted for post-treatment assessments, at least three attempts (two phone calls and a certified letter) will be made to locate the study subject, and these efforts will be documented. If the subject cannot be located, the subject's lost to follow-up status will be documented in the EDC and they will be exited from the study.

Should the subject expire, adverse event and study exit/withdrawal forms should be completed. Physician assessment is required to determine if the cause of death was possibly or definitely related to the JAVELIN Peripheral IVL Catheter. If available, copies of the death certificate and/or an autopsy report should be included in the research records. The Investigator may need to provide written notification to the IRB upon the death of the study subject, dependent on the IRB policies. Associated regulatory bodies may also be required to be notified depending on local jurisdiction and relatedness to the study device and procedures.

 SHOCKWAVE <small>MEDICAL INC</small>	No.: CP 67398	REV. C
	TITLE: FORWARD PAD IDE Study Protocol	
	CLASS: CLINICAL PROTOCOL	PAGE 33 OF 65

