9.3 Sample Size Determination

The sample size determination for the Mini S Study and FORWARD PAD IDE pooled analysis is based on the Primary Safety Endpoint of MAE at 30 days and the Primary Effectiveness endpoint of Technical Success.

Primary Safety Hypothesis:

$$H_0: \Pi_S > PG_S \text{ vs. } H_A: \Pi_S \leq PG_S$$

where Π_S is the proportion of patients who experience an MAE within 30 days of the index procedure and PG_S is the Safety Performance Goal (PG).

The assumptions for the sample size calculations are listed below.

- Expected 30-day MAE rate of 2.0% = Π_S
- Performance Goal for 30-day MAE of 11.2% = PG_S
- One-sided statistical significance level of 0.025 = α
- The hypothesis will be tested using a one-sided Exact Binomial Test
- Statistical power of 96.5%

Primary Effectiveness Hypothesis:

$$H_0: \Pi_E \leq PG_E \text{ vs. } H_A: \Pi_E > PG_E$$

where Π_E is the proportion of patients with Technical Success and PG_E is the Effectiveness Performance Goal (PG).

The assumptions for the sample size calculations are listed below.

- Expected Technical Success rate of 97.0% = Π_E
- Performance Goal for Technical Success of 85.0% = PG_E
- One-sided statistical significance level of 0.025 = α
- The hypothesis will be tested using a one-sided Exact Binomial Test
- Statistical power of 98.1%

The performance goals are based on previous studies of peripheral IVL and benchmark plaque modification devices. Refer to the statistical analysis plan (SAP) for details.

A one-tailed scenario was used to assess the minimum sample size needed to detect a difference in the assumed true rate of safety (2%) versus the performance safety goal of 11.2%. The same calculation was done for the assumed true rate of effectiveness (97%) versus the performance effectiveness goal of 85%. The sample size of 90 subjects provides a study-wide power of 94.7% to meet both the safety and effectiveness endpoints. The study will be deemed a success if the null hypothesis is rejected for both the primary safety and effectiveness measures. No adjustments for multiplicity are needed.

 SHOCKWAVE <small>MEDICAL INC</small>	No.: CP 67398	REV. C
	TITLE: FORWARD PAD IDE Study Protocol	
	CLASS: CLINICAL PROTOCOL	PAGE 37 OF 65

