9.4 Analysis Populations and Poolability

The primary analysis population for the FORWARD PAD IDE study will be the Intent-to-Treat (ITT) cohort which includes all enrolled subjects.

The FORWARD PAD IDE study is being conducted to supplement enrollment in the ongoing Mini S Study described in Section 3.1.3; data from subjects enrolled under the IDE protocol will be pooled with data from the Mini S Study to reach a total sample size of 90 subjects. Results for the first 90 consecutively enrolled subjects across both studies (with a minimum of 50% of subjects enrolled from in the US) will comprise the primary analysis cohort and will be submitted to support a Premarket Notification 510(k) application.

Justification of poolability is based on the following: The Mini S Study and the FORWARD PAD IDE Study protocols share the same eligibility criteria, data collection requirements and IVL treatment algorithm; both studies utilize the same electronic data capture system, are monitored with 100% source document verification, and include an independent angiographic core lab, independent clinical events committee (CEC) for endpoint adjudication of MAE and data safety monitor (DSM); and both studies use the XTR and FLX configurations of the JAVELIN catheter.

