Clinical endpoints include repeat revascularization procedures on target lesions/vessels, death, target limb amputations, and safety endpoints including Major Adverse Events, that occur within a specific time period. For each reporting period, the event rate will be defined as the number of subjects experiencing the event divided by the number of evaluable subjects. A subject will be considered evaluable for a reporting period if the study day of last contact is at or after the lower limit of the reporting window on the snapshot date. Acceptable study contacts include a study visit, adverse event, CEC adjudicated event date, image date, or other verifiable event that occurs during the active follow-up of a subject. Active follow-up ends when a subject completes the study, withdraws consent, or is considered lost to follow-up.

B. Core Lab Endpoints

Core lab endpoints include the endpoints that are determined by core lab assessment (duplex ultrasound or angiography), such as restenosis measured by duplex ultrasound or residual stenosis by angiography. Core lab endpoints rely on the actual evaluable assessment. If the scheduled assessment is not completed or the data are not evaluable (i.e., not readable or non-diagnostic), it will be treated as missing value and excluded from the analysis. Data will be used for subjects who have an evaluable (readable or diagnostic) scheduled duplex ultrasound.

C. Determination of Primary Patency Composite Effectiveness Endpoint

Primary patency contains both core lab endpoint (by visit) and clinical/safety endpoint (by cut-off days); the event of the individual component will be determined first, and the composite endpoint will then be determined.

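### A withdrawing subject can have a recorded MAE kept out of the database, against the ITT statements, and at the decision boundary one such removal changes the primary safety result

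*Protocol*

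**What the plan says.** Protocol 7.9.1 sets out three ways of leaving the study.

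- **Written request.** Data obtained before withdrawal may be submitted to the sponsor and "be included in the study database, unless otherwise requested by the subject in writing". Inclusion is permitted rather than required, and the subject can refuse it.
- **Physician.** "Subjects may be withdrawn with the medical discretion of the physician". No criteria are given.
- **Loss to follow-up.** When at least three attempts (two calls and a certified letter) have failed, "the subject's lost to follow-up status will be documented in the EDC and they will be exited from the study". Nothing says that contact is tried again at a later visit.

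The primary analysis population in Protocol 9.4 is "the Intent-to-Treat (ITT) cohort which includes all enrolled subjects". SAP 6.1 likewise includes every subject in whom the catheter was introduced and calls the analysis intent-to-treat.

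SAP 9.3 allows no imputation. It limits the 30-day MAE denominator to subjects with at least 23 days of follow-up plus any with an earlier event. SAP Appendix A repeats that rule and adds: "Active follow-up ends when a subject completes the study, withdraws consent, or is considered lost to follow-up".

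Protocol 7.9 says withdrawn subjects are not replaced. SAP 8 defines the primary cohort as the first 90 consecutively enrolled evaluable subjects.

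**The concern.** In an intent-to-treat analysis, a subject's data should not be removable once the outcome is known. A subject who has had a revascularization or an amputation may be more likely than others to withdraw and to ask for deletion, so the missingness can depend on the endpoint. Neither document specifies a sensitivity or tipping-point analysis that would show whether the result depends on such removals.

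The other two routes raise a different and weaker problem. The study treatment is one completed procedure, so a subject who is exited afterwards leaves outcome follow-up only. An MAE that occurs later may never be captured, and an early exit forfeits the 6- and 12-month MAE status and the single 12-month duplex scan on which patency depends.

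**Working it through.** **Inputs.** Protocol 9.3 and SAP 6.1 give "One-sided statistical significance level of 0.025", a performance goal of 11.2%, an expected MAE rate of 2.0% and 90 subjects. On the test: "The hypothesis will be tested using a one-sided Exact Binomial Test". The day-23 limit is the lower edge of the 30-day window (30 − 7).

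**Formula.** For x events in n subjects, p = P(X ≤ x | n, 0.112) = Σ (k = 0 to x) C(n,k) · 0.112^k · 0.888^(n−k). The test passes if p ≤ 0.025.

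**Reproducing the plan.** At n = 90, P(X ≤ 4) = 0.0218 and P(X ≤ 5) = 0.0537, so at most 4 events pass. This agrees with the passing range of 0.0–4.4% in SAP Appendix B (4/90 = 4.4%). Power at a true rate of 2.0% is P(X ≤ 4 | 90, 0.02) = 0.9652, the stated 96.5%. Multiplied by the effectiveness power of 0.9812, it gives 0.9471, the stated 94.7%.

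**Effect of losing subjects.**

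| Situation | Events/n | p | Upper 97.5% bound | Result |
|---|---|---|---|---|
| Five MAEs, all data kept | 5/90 | 0.0537 | 12.49% | fail |
| One MAE subject removed | 4/89 | 0.0236 | 11.11% | pass |
| One MAE subject removed, next evaluable subject event-free | 4/90 | 0.0218 | 10.99% | pass |
| Four MAEs, two event-free subjects lost | 4/88 | 0.0255 | 11.23% | fail |

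With the one-sided 95% bound that Protocol 9.2.1 reports, the flip is the same: 11.33% at 5/90 is above the goal, and 9.99% at 4/89 is below it.

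**How often the boundary is reached.** The chance of exactly five events in 90 is 2.5% at the planned 2.0%, 6.8% at 2.8% (the SAP's random-effects estimate) and 15.8% at 4.4% (its common-effect estimate). Each figure must still be multiplied by the unknown chance that one of the five affected subjects is lost.

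**Upper limit on the type I error.** If one MAE subject were always removed, five true events would pass. The error at a true rate of 11.2% would then rise from 0.0218 to 0.0537.

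**Which route does what.**

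- *Written request:* takes out data already recorded, including an MAE. The SAP's protection for earlier events does not help if those events are not in the database.
- *Physician withdrawal or loss to follow-up, event already recorded:* the subject stays in the numerator and the denominator (SAP 9.3, Appendix A).
- *Either of these, last contact before day 23 and no event:* the subject leaves the denominator. If an MAE follows by day 30 and is not captured, the analysis shows 4/89 where complete follow-up would have shown 5/90.
- *Either of these, last contact from day 23:* the subject counts as event-free, whatever happens in the days up to 30 that were not observed.

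**The case against.** A reader might infer that all three routes can erase a known MAE. The documents do not support that: SAP 9.3 and Appendix A keep any subject with an earlier event, so only the written request can do it. A reader might also infer that physician withdrawal ends event capture. Appendix A lists completion, withdrawal of consent and loss to follow-up, and does not list withdrawal by the physician. What happens to such a subject is left unclear rather than stated.

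There are real safeguards. Three attempts are a minimum. A missed 30-day visit is not by itself an exclusion, because Appendix A accepts an adverse event, an image date or another verifiable event as contact. SAEs reach the sponsor within 2 business days (Protocol 10.4.2), missing endpoint data are queried (SAP 10.2), and source verification is 100% (Protocol 9.1). These limit undocumented loss, but they do not cure a deletion request.

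It is also fair to say that any exact binomial rule turns on one event at its cutoff, which is not a fault of 7.9.1, and that losing event-free subjects works against the sponsor. Both points stand. They limit how much weight the flip can carry, but they do not justify leaving inclusion of recorded outcomes optional.

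Finally, Protocol 7.9.1 governs the IDE subjects only. At least half of the 90 must come from the US, so up to 45 may come from the Mini S Study, whose protocol is not among the documents. SAP 7 says the follow-up procedures are shared, but the Mini S withdrawal wording cannot be checked. Nor can the consent template, which is a separate attachment.

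**Conclusion.** The point holds in a limited form. The written-request clause conflicts with the ITT statements and is the only route by which a recorded MAE can leave the primary safety test. The other two routes can thin the denominator before day 23 and leave later events uncaptured, and their larger cost falls on the 6- and 12-month endpoints.

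The reversal from fail to pass requires exactly five events in 90 and the loss of a subject with an MAE. It should not be read as a likely result or as evidence that the test is generally unsafe. The error can go either way: two event-free losses turn a pass at 4/90 into a fail at 4/88, if the lost subjects are not made up.

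Whether they are made up is itself unsettled. No replacement, all enrolled subjects, and the first 90 evaluable subjects cannot all describe the same cohort.

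The p-values rest on the plan's own test and goal. No dropout or deletion rate is given, so the probability of the full sequence cannot be calculated.

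**What to change.** 1. In Protocol 7.9.1, state that data collected up to withdrawal stay in the database and in the analysis, and that a written request stops future collection only. Bring the consent wording into line.
2. State that a physician's decision to change care does not by itself end outcome follow-up. Removing physician withdrawal altogether would go further than the problem requires.
3. Keep subjects who miss a visit in follow-up, and repeat contact attempts at each later visit window before classing them as lost. Align the active follow-up sentence in SAP Appendix A, and say there how physician withdrawal is treated. This step protects the 6- and 12-month endpoints; it does little for the 30-day test.
4. Reconcile the ITT statements (Protocol 9.4, SAP 6.1), the no-replacement rule (Protocol 7.9) and the first 90 evaluable subjects (SAP 8).
5. Add a sensitivity analysis of the 30-day MAE test that counts enrolled subjects without 23-day follow-up as events. With 90 enrolled subjects it passes if MAEs plus such subjects total at most 4. At the planned rate 90 × 0.02 = 1.8 events are expected, which leaves room for about two.

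The cost is protocol, consent and SAP wording, a few extra contact attempts, and a sensitivity result that may be less favourable than the primary one. No additional subjects or procedures are needed.

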8.0 BENEFITS AND RISKS

8.1 Benefits

There may be no additional benefit from participation since patients can receive IVL treatment with a commercially available device per standard of care. The study will provide safety and effectiveness data associated with treatment of calcified arteries using the JAVELIN IVL Catheter. These clinical results may inform physicians in determining the optimal treatment strategy for this patient population.

8.2 Risks

For detailed information on the risks of the device(s) used in the study procedure, including a complete list of contraindications, warnings, precautions, and potential adverse effects, please refer to the Instructions for Use (IFU) for the JAVELIN Peripheral IVL Catheter. It is important to ensure that the IFU referred to represents the generation of the device used in the study procedure. Unanticipated risks can occur.

Possible adverse effects are consistent with standard intravascular procedures. Risks identified as unique to the device and its use are outlined in the IFU for the JAVELIN Peripheral IVL Catheter. They include:

- Allergic/immunologic reaction to the catheter material(s) or coating
- Device malfunction or failure

